6.2.4 Dose Delays and Modifications

Cycles are 28 days in duration regardless of dose interruption unless toxicity recovery period before entering next cycle includes Day 1 of the next cycle. For patients with dose interruption, next cycle will start with resumption of study drug. In this situation, disease assessments should continue to follow the original schedule.

For all parts of this study, toxicities such as nausea, vomiting, or diarrhea or dizziness or dehydration related to these symptoms, may be managed with increased supportive care, including hydration, electrolyte repletion and the use of anti-emetics such as serotonin type 3 (5-HT3) antagonists and/or anti-diarrheals such as loperamide as appropriate.

Treatment for the first cycle should commence only if all the inclusion and exclusion criteria are met. Subsequently, the selpercatinib dose may be delayed/modified if the patient experiences a Grade 3 or greater clinical AE considered to be at least possibly related to selpercatinib.

Dose reductions should be made according to the following parameters using the dose reduction table below.

- Interrupt dosing for CTCAE v5.0 Grade 3 or greater adverse events or Grade 2 adverse events not resolved within 48 hours with appropriate supportive care (e.g., nausea not improved with antiemetics) and considered intolerable by the patient or the investigator.
- For selpercatinib related specific adverse events (hypersensitivity, liver function test abnormalities, thrombocytopenia, and hypertension), see dose adjustments below in Sections 6.2.3 (any concerns of these recommended actions in clinical practice should be discussed with the Sponsor, who may permit adjust actions).
- Dose modifications for ECG changes are described in Section 8.2.1. If a patient receiving selpercatinib experiences QTCF > 500 msec despite two dose reductions and if the investigator deems it in the best interest of the patient, the patient may continue treatment with study drug with CRP/CRS approval. In addition, Lilly may request a copy of the ECGs for adjudication.
- Upon resolution (or return to patient's baseline) of adverse events at least possibly related to treatment, reduce the dose as follows:
 - If previously receiving dose level 1, resume treatment at dose level -1
 - If previous receiving dose level -1, resume treatment at dose level -2

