- k. Obtain a single pre-dose ECG during Screening and again on C1D1. If the C1D1 pre-dose QTcF > 470 msec (QTcF = QT (msec)/RR^{1/3}), where RR (msec) = $60 \times 1000/\text{BPM}$), the Sponsor should be notified prior to dosing to determine whether the patient remains eligible. On C1D8, C2D1 and thereafter, perform a single ECG at 2 hours (± 10 minutes) post-selpercatinib dosing. On C1D8 PK collection, an extra ECG should be timed prior to the PK sample being drawn. Dose patients in the visit to ensure accuracy of timing. If any ECG demonstrates QTcF 481-500 msec, perform an additional ECG at the same day, specific time judged by investigator. If any ECG demonstrates QTcF > 500 msec, repeat the ECG twice (triplicate in total) at the same day, specific time judged by investigator, and manually review to confirm accuracy. If QTcF > 500 msec is confirmed on 2/3 ECGs, hold selpercatinib and assess for alternative causes (concomitant medications, electrolyte abnormalities). Potassium should be > 4 mEq/L and $< \text{ULN}$ and magnesium and calcium should be within normal limits. selpercatinib may be resumed at one reduced dose level when QTcF has returned to baseline value, and with continued ECG monitoring as noted in the assessment schedule.
- l. Repeat only if EOT reading showed treatment-emergent abnormalities.
- m. For women of childbearing potential: Serum pregnancy test at Screening, serum or urine pregnancy test at Day 1 of every cycle (-2 days) (surgically sterilized females or those who have not experienced menses for at least 2 years are not required to be tested i.e., post-menopausal women who have not had menses within the last 12 months but have had menses within the last 24 months will be required to have a serum pregnancy test performed.). If screening testing is performed ≤ 7 days prior to C1D1, repeat testing does not need to occur on C1D1.
- n. Hemoglobin, hematocrit, RBC count, WBC count with differential (neutrophils [count and percent] and lymphocytes, monocytes, eosinophils, basophils [percent]), and platelet count). Patients found to have treatment-emergent hematologic toxicity of Grades 3 or 4 will be monitored at least weekly until resolution. If screening testing is performed ≤ 7 days prior to C1D1, repeat testing does not need to occur on C1D1.

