8.2 Safety Assessments

8.2.1 *Electrocardiograms*

ECG monitoring should be performed as outlined in the SoA (Table 7-1). The actions below should be taken if the triplicate average QTcF is greater than 500 msec.

- Manually review to confirm accuracy
- Assess for alternative causes (concomitant medications, electrolyte abnormalities, presence of pacemaker). Potassium should be ≥ 4 mEq/L and $<$ ULN and magnesium and calcium should be within normal limits.
- Institutional guidelines or SOC measures for management of QTcF interval >500 msec and/or associated arrhythmias should be initiated.
- Clinical chemistry should be assessed and if electrolytes are abnormal, they should be repeated as indicated.

If a patient experiences a QTcF interval >500 msec and if the investigator deems it in the best interest of the patient, the patient may continue treatment with study drug (with a dose reduction).

8.2.2 **Clinical Safety Laboratory Assessments**

- Investigator sites may use local laboratories to determine patient eligibility and treatment decisions.
- In addition, blood will be collected,
 - See [Appendix H](#) for the list of clinical laboratory tests to be performed and [Table 7-1](#) (Schedule of Activities) for the timing and frequency.
 - The investigator should review any clinically significant abnormal laboratory findings and assess relevance to patient care. If the laboratory findings are clinically significant, the investigator should document the findings as an adverse event in the case report form. The laboratory reports must be filed with the source documents. Clinically significant abnormal laboratory findings are based on investigator judgement.
- Regardless of whether or not central or local laboratory tests are used to determine patient care decisions, all laboratory tests with values considered clinically significantly abnormal during participation in the study or until completion of SFU should be repeated until the values return to normal or baseline or are no longer considered clinically significant by the investigator.
 - If such values do not return to normal/baseline within a period of time judged reasonable by the investigator, the etiology should be identified, and the sponsor notified.
 - All protocol-required laboratory assessments, as defined in [Appendix H](#), must be conducted in accordance with the laboratory manual and the SoA.

8.2.2.1 **Hepatic Safety Monitoring**

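### Table 7-1 note k and Section 8.2.1 use different triggers for QTcF above 500 msec, and no passage says whether continuing at a reduced dose comes only after note k's hold

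*Protocol*

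**What the plan says.** Three places in the protocol deal with a QTcF above 500 msec.

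- **Table 7-1, note k.** A reading above 500 msec is repeated twice, giving a triplicate, and is reviewed manually. Then: "If QTcF > 500 msec is confirmed on 2/3 ECGs, hold selpercatinib" and look for other causes. On restart: "selpercatinib may be resumed at one reduced dose level when QTcF has returned to baseline value".
- **Section 8.2.1.** It opens with "ECG monitoring should be performed as outlined in the SoA" and then sets its own trigger: "The actions below should be taken if the triplicate average QTcF is greater than 500 msec". The actions are manual review, a search for other causes, electrolyte checks, and "Institutional guidelines or SOC measures for management of QTcF interval >500 msec and/or associated arrhythmias should be initiated". It closes by saying that, for a QTcF above 500 msec and where the investigator judges it best, "the patient may continue treatment with study drug (with a dose reduction"). It mentions neither a hold nor a return to baseline.
- **Section 6.2.4.** "Dose modifications for ECG changes are described in Section 8.2.1". The same list has a general rule, "Interrupt dosing for CTCAE v5.0 Grade 3 or greater adverse events", followed by a one-level dose reduction once an event at least possibly related to treatment has resolved or returned to baseline. Its own QTcF sentence covers only a value above 500 msec despite two dose reductions, where treatment may go on with approval from the sponsor's physician or scientist (CRP/CRS).

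**The concern.** A site that takes three ECGs after a reading above 500 msec finds two tests for what counts as confirmed. Note k counts tracings; Section 8.2.1 averages them. The site also finds two descriptions of what follows: one orders a hold, and the other allows treatment to continue at a lower dose without mentioning a hold. The pointer in Section 6.2.4 leads to the description without the hold.

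At stake is uniform handling of a cardiac safety signal across about 40 sites. The rule may well be needed: Section 1.5 reports Grade 3-4 QT prolongation in 4.0% of patients in the earlier study (2.8% related).

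Two smaller mismatches sit in the same text. Note k wants potassium above 4 mEq/L, whereas Section 8.2.1 accepts 4 or more. Note k's QTcF formula, as extracted, takes RR in msec.

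**Working it through.** **1. The triggers on the same three ECGs.** Note k is met when at least 2 of 3 readings exceed 500 msec. Section 8.2.1 is met when (x1 + x2 + x3)/3 exceeds 500 msec.

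| Triplicate (msec) | Readings >500 | Mean | Note k | Section 8.2.1 |
|---|---|---|---|---|
| 505/505/480 | 2 | 1490/3 = 496.7 | met | not met |
| 505/505/491 | 2 | 1501/3 = 500.3 | met | met |
| 520/495/495 | 1 | 1510/3 = 503.3 | not met | met |

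With two readings of 505, the average exceeds 500 only if the third is above 1500 − 1010 = 490. With two readings of 495, one reading above 1500 − 990 = 510 meets the average alone. Neither trigger implies the other.

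**2. How often they disagree.** The documents give no within-patient ECG variability, so this cannot be derived. As an illustration, assume independent normal readings and a first reading above 500 msec. The share of triplicates on which the triggers disagree is then, by simulation:

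| True mean (msec) | SD 5 | SD 10 | SD 15 |
|---|---|---|---|
| 490 | 3.3% | 16.8% | 20.4% |
| 495 | 15.8% | 20.5% | 20.1% |
| 500 | 16.4% | 16.4% | 16.3% |
| 505 | 2.9% | 8.2% | 10.7% |
| 510 | 0.1% | 2.6% | 5.8% |

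The range, 0.1% to 20.5%, reflects the assumptions and not the trial.

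**3. The actions side by side.**

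| | Note k | Section 8.2.1 | Section 6.2.4, general rule |
|---|---|---|---|
| Hold | ordered | not stated | ordered for Grade 3 or greater |
| Condition for restart | QTcF back to baseline | not stated | resolution or return to baseline |
| Dose afterwards | one level lower | reduced | one level lower |

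Section 6.2.4's general sequence matches note k. However, the same list sends ECG changes separately to Section 8.2.1, which could be read as taking them out of the general rule. Whether QTcF above 500 msec is Grade 3 depends on CTCAE, which the documents do not reproduce.

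**4. Whether the rule will be used at all.** Apply the Section 1.5 rates to 75 patients.

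- At 2.8%: 75 × 0.028 = 2.1 expected; 1 − 0.972^75 = 0.881.
- At 4.0%: 75 × 0.040 = 3.0 expected; 1 − 0.960^75 = 0.953.

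This assumes that rates pooled over nine dose levels carry over and that Grade 3-4 stands in for QTcF above 500 msec. It counts patients who might meet the rule, not patients whom the inconsistency would affect.

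**5. The formula in note k.** With RR in msec, RR = 60 × 1000/BPM = 1000 × (60/BPM). The cube root of 1000 is 10, so the result is one tenth of the value with RR in seconds. For QT 440 msec at 75 bpm it is 440/800^(1/3) = 47.4, against 440/0.8^(1/3) = 474.0. The extracted line has one closing parenthesis too many, so a character may have been lost in extraction.

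**The case against.** The best defence is that the action conflict is silence rather than contradiction. Section 8.2.1 nowhere tells a site not to hold. Its permission to continue can mean that the patient need not be taken off drug permanently, which is the natural sense of the similar permission in Section 6.2.4 after two reductions. Section 8.2.1 also depends on the schedule: it orders no triplicate itself, so a site with three ECGs has normally come through note k or the Cycle 1 Day 8 text in Section 7.2. A site can obey everything by holding, working up, and resuming at a lower dose after recovery, as Section 6.2.4's general rule also implies.

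Much of this stands. A reader might infer that the protocol tells sites to keep dosing through a confirmed QTcF above 500 msec; the documents do not support that. A reader might also infer that two or three patients would be mishandled. That fails too: the count needs Grade 3-4 as a proxy for QTcF above 500 msec, and if the proxy holds, Section 6.2.4's Grade 3 rule supplies a hold. Even 3.0 patients with one triplicate each, at the highest tabulated disagreement, give 3.0 × 0.205 = about 0.6 patients with conflicting triggers.

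What the defence does not remove is the trigger mismatch, or the lack of any sentence making the hold a condition for continuing.

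**Conclusion.** The inconsistency is real and is in current text. The triggers differ as a matter of arithmetic, and no passage says which one governs. The actions are compatible on a reasonable reading, but the protocol leaves that reading to the site, and its own pointer leads to the section that omits the hold.

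The size cannot be stated from the documents; the simulated range rests wholly on assumed means, SDs and independence. Disagreement is confined to triplicates whose readings fall on both sides of 500 msec. The efficacy analyses are not affected.

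The side points are minor. The potassium limits differ only at exactly 4 mEq/L. A reader might infer from the formula that the trial's QTcF values are wrong. The documents do not support that: exclusion criterion 27 names Fridericia's formula, the limits are on the usual msec scale, and the line may be damaged by extraction.

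**What to change.** Use note k's rule, in the same words, in note k and Section 8.2.1: QTcF above 500 msec on 2 of 3 ECGs, hold, and restart one dose level lower after return to baseline. State in Section 8.2.1 that continuing at a reduced dose applies only after that hold. Have Section 6.2.4 refer to this single rule. If the sponsor prefers the triplicate average on clinical grounds, the same requirement applies: one trigger and one sequence everywhere.

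In the same edit, settle the potassium limit and check note k's formula against the source document. If it is printed as extracted, define RR in seconds as 60/BPM.

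The cost is a protocol clarification and a notice to sites. No data, visits or efficacy analyses change.

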7.1 Screening Period

The following procedures must be obtained within 28 days of C1D1 unless otherwise noted. Patients who cannot complete the procedures within the screening window may be rescreened, and certain screening procedures, in investigator's opinion, may not need to be repeated, including certain procedures that were obtained as part of the patient's standard care prior to providing informed consent for this study (provided the patient provides informed consent), with the approval of the Sponsor.

- Informed Consent.
- Medical, surgical, and malignancy history, including histologic confirmation of solid tumor, primary and metastatic diagnosis dates, prior treatments for the malignancy, etc.
- Submission of redacted Molecular Pathology Report(s) describing *RET* and other alterations, to Sponsor or designee.
- Confirmation of availability of archived tumor tissue to be submitted, either tumor block (preferred) or $\sim 10 \times 5 \mu\text{m}$ unstained slides. If archived tumor tissue is not available or is of insufficient quantity or quality, a fresh tumor biopsy could be obtained prior to selpercatinib. If patients cannot provide sufficient tumor tissue sample, patients still can be enrolled after discussion between sponsor and investigator and get sponsor's approval. Physical examination, including relevant review of systems, body weight and height, and ECOG performance status (refer to [Appendix F](#)).
- Vital signs, including systolic and diastolic blood pressure, heart rate, respiratory rate, and body temperature.
- Obtain a single ECG during Screening.
- Serum pregnancy test for women of childbearing potential (surgically sterilized females or those who have not experienced menses for at least 2 years are not required to be tested i.e., post-menopausal women who have not had menses within the last 12 months, but have had menses within the last 24 months will be required to have a serum pregnancy test performed.).
- Hematology, details described in [Appendix H](#).
- Serum chemistries (non-fasting), details described in [Appendix H](#).
- Coagulation: (as described in Section 7.1).
- Thyroid panel, including thyroid stimulating hormone (TSH), free triiodothyronine (FT₃), and free thyroxine (FT₄).
- Urinalysis, details described in [Appendix H](#).
- Calcitonin, CEA: for patients with MTC only. For each patient, all tests for calcitonin and CEA should be performed in the same laboratory to minimize intra-patient, lab-to-lab variability in their measurement.
- Thyroglobulin: for patients with non-MTC thyroid cancers only (unless not measurable due to presence of anti-thyroglobulin antibodies). For each patient, all tests for

thyroglobulin should be performed in the same laboratory to minimize intra-patient, lab-to-lab variability in their measurement.

- Blood cortisol, adrenocorticotropic hormone (ACTH), 24-hour urine for free cortisol: optional for patients with Cushing's disease related to their cancer.
- Baseline disease assessment with radiographic tumor measurements using:
 - All patients: computerized tomography (CT) or magnetic resonance imaging (MRI) of chest, abdomen, and pelvis, and any other areas with suspected disease involvement, within 28 days of C1D1.

Note: Accurate documentation of prior irradiation including exact locations/sites must be provided.

- All fusion-positive solid tumor patients, patients with a history of CNS metastases, or other patients if clinically indicated: brain imaging, MRI with and without contrast is preferred, CT with and without contrast is acceptable if MRI is medically contraindicated, within 28 days of C1D1.
- For each modality, intravenous (IV) and oral contrast should be utilized where applicable unless medically contraindicated.
- If CT/positron emission tomography (PET) is utilized, the CT component of CT/PET must be of the same quality as a dedicated diagnostic CT scan, i.e., with IV and oral contrast and 5 mm or less slice thickness.
- Bone scan required only for patients with nonmeasurable bone disease identified at baseline or if clinically indicated.

Notes:

- In patients with thyroid and other head and neck cancers, imaging of the relevant areas (e.g., neck, skull base) is required at baseline; other areas of scanning may differ depending on disease type. Refer to the separate Imaging Manual that will be distributed to the sites for details.
- Additional scans can be performed as needed to evaluate potential sites of disease.
- Disease assessments will utilize RECIST 1.1 (refer to Section 7.7.1).
- Guidelines on the technical parameters of how scans should be performed will be provided in the Imaging Manual
- Concomitant, ongoing medications plus those administered within 14 days prior to the planned start of treatment.

7.2 Cycle 1

The procedures listed below will be performed at the indicated intervals. Observations, routine laboratory tests, and HRQoL assessments will be performed prior to selpercatinib dosing on that day unless otherwise indicated. Routine clinic visits and C1D1 evaluations performed within - 2 days of the nominal visit day will not be considered protocol deviations, with the exception of ECGs, PKs, and vital signs, which must be performed relative to the dose of selpercatinib on that day as indicated below.

Day 1

- Symptom-directed physical examination, weight, and ECOG.
- Vital signs: pre-dose (up to 4 hours pre-dose, as close to dosing as possible is preferred) and 2 hours post-dose (± 30 minutes). Vital signs should be performed prior to collection of PK blood sample drawn at that time point.
- Resting 12-lead ECG: pre-dose (up to 4 hours pre-dose).
- Serum or urine pregnancy test for women of childbearing potential (surgically sterilized females or those who have not experienced menses for at least 2 years are not required to be tested i.e., post-menopausal women who have not had menses within the last 12 months, but have had menses within the last 24 months will be required to have a serum pregnancy test performed).
- Hematology (as described in [Appendix H](#)).
- Serum chemistries (as described in [Appendix H](#)).
- Blood sample of intensive PK (2 mL whole blood) for a total 12 subjects: pre-dose, and post-dose at 1 hour (± 15 minutes), 2 hours (± 15 minutes), and 4 hours (± 15 minutes), 8 hours (± 30 minutes) and 12 hours (± 30 minutes). Exact clock time (24h format) of sample collection and of dose administration should be recorded.
- Blood sample of PopPK (2 mL whole blood) for all enrolled subjects: each cycle D1 predose.
- Coagulation (as described in [Section 7.1](#)).
- Calcitonin, CEA: for patients with MTC only. For each patient, all tests for calcitonin and CEA should be performed in the same laboratory to minimize intra-patient, lab-to-lab variability in their measurement.
- Thyroglobulin: for patients with non-MTC thyroid cancer only (unless not measurable due to presence of anti-thyroglobulin antibodies). For each patient, all tests for thyroglobulin should be performed in the same laboratory to minimize intra-patient, lab-to-lab variability in their measurement.
- Blood cortisol, ACTH, 24-hour urine for free cortisol: optional for patients with Cushing's disease related to their cancer. If done, urine collection should begin pre-dose.
- Dispense selpercatinib.
- Selpercatinib administration.
- Outpatient diaries for recording daily selpercatinib dosing, H2 blockers and antacids.
- AEs.
- Concomitant medications.
- Patient-reported outcomes to be completed pre-dose:
 - For MTC patients with diarrhea present at baseline: bowel diary.
 - European Organization for Research and Treatment of Cancer Quality of Life Questionnaire-Core 30 (EORTC QLQ-C30).

Day 8

- Symptom-directed physical examination, weight, and ECOG.
- Vital signs: pre-dose (up to 4 hours pre-dose, as close to dosing as possible is preferred) and 2 hours post-dose (± 30 minutes). Vital signs should be performed prior to collection of PK blood sample drawn at that time point.
- Resting 12-lead ECG: perform a single ECG at 2 hours (± 10 minutes) post-selpercatinib dosing. On C1D8 PK collection, an extra ECG should be timed prior to the PK sample being drawn. If any ECG demonstrates QTcF 481-500 msec, perform an additional ECG at the same day, specific time judged by investigator. If any ECG demonstrates QTcF > 500 msec, repeat the ECG twice (triplicate in total) at the same day, specific time judged by investigator, and manually review to confirm accuracy.
- Hematology (as described in [Appendix H](#)).
- Serum chemistries (as described in [Appendix H](#)).
- Blood sample of intensive PK (2 mL whole blood) for a total 12 subjects: pre-dose, and post-dose at 1, 2 and 4 hours (± 15 minutes), and 8 hours (± 30 minutes). Exact clock time (24h format) of sample collection and of dose administration should be recorded.
- Outpatient diaries for recording daily selpercatinib dosing, H2 blockers, and antacids.
- AEs.
- Concomitant medications.
- For MTC patients with diarrhea present at baseline: bowel diary.

Day 15

- Symptom-directed physical examination, weight, and ECOG.
- Vital signs: pre-dose (up to 4 hours pre-dose, as close to dosing as possible is preferred).
- Hematology (as described in [Appendix H](#)).
- Serum chemistries (as described in [Appendix H](#)).
- Thyroid panel, including TSH, FT₃, and FT₄.
- Urinalysis.
- Calcitonin, CEA: for patients with MTC only. For each patient, all tests for calcitonin and CEA should be performed in the same laboratory to minimize intra-patient, lab-to-lab variability in their measurement.
- Thyroglobulin: for patients with non-MTC thyroid cancer only (unless not measurable due to presence of anti-thyroglobulin antibodies). For each patient, all tests for thyroglobulin should be performed in the same laboratory to minimize intra-patient, lab-to-lab variability in their measurement.
- Blood cortisol, ACTH, 24-hour urine for free cortisol: optional for patients with Cushing's disease related to their cancer. If done, urine collection should begin pre-dose.
- Outpatient diaries for recording daily selpercatinib dosing, H2 blockers, and antacids.
- AEs.
- Concomitant medications.

- For MTC patients with diarrhea present at baseline: bowel diary. Two patient bowel diary cards will be dispensed on C1D15, another card will be used on C1D22.

Day 22

- Telephone contact for safety.

